
Study Objectives

Primary Objectives

The **primary objective** of this study is to evaluate the current management approach with “intermediate” or “therapeutic” doses of tinzaparin for thromboprophylaxis in hospitalized patients, non on ICU organ support, with confirmed COVID-19.

- Evaluate incidence of thrombotic events
- Evaluate incidence of bleeding events

Secondary Objectives

The **secondary objective** is to

- ✓ Examine the course of illness of COVID-19 via measure of clinical improvement and/or survival, assessed at pre-specified time points post admission

Patients demographic & somatometric data, medical history (thrombosis & bleedings related history, co-morbidities, chronic use of medications, results of laboratory tests etc.), clinical parameters, anticoagulant prophylaxis dose & duration, efficacy (thrombosis events), safety (bleedings), imaging and laboratory tests results and information about other supportive treatment will be recorded; more than one outcomes could be recorded.

Based on analysis of collected data, **we'll examine correlations between thromboprophylaxis approach, patients' profiles and clinical outcomes.**

Study Endpoints

Primary Endpoints

- **Incidence of thrombotic events** (total & per type e.g. PE, DVT, symptomatic, incidental, proximal, distant etc.)
- **Incidence of bleeding events** (total & per type e.g. Major, CRNMB and minor)

Secondary Endpoint

- **World Health Organization (WHO) progression scale** (range from 0 (healthy) to 10 (death); values below or equal to 5 correspond to the absence of any oxygen supply beside nasal or facial mask)
- **Length of hospital stay (days)**

Study Design

This is a retrospective phase IV, observational, non-interventional cohort study that aims to collect data regarding thromboprophylaxis management in high thrombotic risk hospitalized, non on ICU, patients with COVID-19 pneumonia. Specifically, we will collect retrospectively data for patients received thromboprophylaxis with tinzaparin, according to current clinical practice, during hospitalization, for one year before the study initiation date, to evaluate safety and efficacy of thromboprophylaxis and to examine possible associations of

patients' profiles with thrombotic and bleeding events and the course of illness in this cohort of patients.

We will collect data retrospectively in paper CRFs, recorded from the treating physicians.

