Additionally, we will assess the association of a panel of laboratory and clinical parameters representing an inflammatory and hemostatic state with VTE and bleeding events and clinical outcomes.

Institutional Review Board will approve the study.

Basic/common markers/parameters

- ✓ *D-Dimers*
- ✓ *C-reactive protein (CRP)*
- ✓ *hemoglobin*
- ✓ *platelets count*
- ✓ *ferritin*
- ✓ *fibrinogen*
- ✓ *SpO₂ in FiO₂ 21%*

In all cases, laboratory and clinical parameters will be collected at 3 time points: at admission/baseline, after one week and at discharge.

Subject Population

Key criteria for Inclusion and Exclusion

Inclusion Criteria

1. Patients admitted to hospital with COVID-19, PCR+ SARS-CoV-2 infection (from any specimen) administered thromboprophylaxis with tinzaparin in intermediate or therapeutic dose
2. Age \geq 18 years
3. Signed informed consent

Exclusion Criteria

1. Patients admitted to ICU with COVID-19, PCR+ SARS-CoV-2 infection (from any specimen)
 2. Age < 18 years
 3. Pregnancy
 4. Current diagnosis or suspicion of pulmonary thromboembolism or deep vein thrombosis
 5. Progression to death was imminent and inevitable within 24 hours from the admission, irrespective of the provision of treatments
 6. Not signed informed consent
-

Study Phases**Screening**

(1) Screening: screening patient files for eligibility, obtaining consent, If eligible

All the data will be gathered from medical records by chart review of the individual patients in a retrospective fashion. There will no direct patient interaction in the study.

Data collection

- Demographic data collection (Gender, Date of birth, Weight, Height, etc.)
- Medical history & pathologic features (Thrombosis & bleedings related history, risk factors, recent surgery, co-morbidities, chronic use of medications, results of laboratory tests, clinical parameters etc.)
- Anti-coagulant administration data
- Thrombotic & bleeding events during course of hospitalization
- Other adverse events related to anticoagulation
- Clinical improvement and/or survival during hospitalization

Timepoints of evaluation

Data of Covid-19 pneumonia patients retrospectively enrolled in the study will be evaluated on a regular basis following the Baseline Visit;

Visit 1 – Baseline, at admission;

Visit 2 - will be after 1 week \pm 2 days

Visit 3 - will be by at discharge from hospital

Statistical analysis & report**Statistical analysis****Statistical and Analytic Plan**

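### The plan defines who may be entered but does not require all eligible admissions, or a random sample, to be entered, so choice of files can shift both primary incidences unnoticed

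*Combined protocol and SAP*

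**What the plan says.** The two primary objectives are "Evaluate incidence of thrombotic events" and "Evaluate incidence of bleeding events", and the primary endpoints are the corresponding incidences, in total and by type.

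Study Design gives the source population and window: "we will collect retrospectively data for patients received thromboprophylaxis with tinzaparin, according to current clinical practice, during hospitalization, for one year before the study initiation". It adds: "We will collect data retrospectively in paper CRFs, recorded from the treating physicians".

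Under Study Phases, the screening step is "screening patient files for eligibility, obtaining consent, If eligible". The same section states: "All the data will be gathered from medical records by chart review of the individual patients in a retrospective fashion". Events are those that occurred during the hospital stay, so they are already in the chart when the file is screened.

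Among the inclusion criteria is "Signed informed consent", and its absence is also listed as an exclusion.

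No section says that all, consecutive or randomly sampled eligible admissions are entered. None names a source list, sets a target number of patients, or asks for a screening log or a count of eligible patients who were not entered.

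**The concern.** An incidence is only as good as the set of patients over which it is taken. In a prospective cohort, patients enter before their events happen. Here the admission is complete, the event is in the file, and the CRFs are to be recorded by the physicians who treated the patients. That these physicians know the outcome is an inference, but a firm one.

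Under the present wording, a site could enter some of its eligible files and leave out others without departing from any sentence of the plan. A file with a pulmonary embolism or a major bleed might be entered more readily because it is remembered, or less readily because it is not offered. Either would pass into the primary estimates and their confidence intervals. The secondary endpoints and the planned associations with patient profile rest on the same files.

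This is separate from whether the eligibility criteria are sound. It concerns which eligible files are opened and entered.

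**Working it through.** **The plan's own figures.** There is nothing to reproduce. The documents give no sample size, expected incidence, number of sites or number of eligible files. All values of p, r and N below are assumptions, shown as ranges.

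**Set-up.** Read each primary incidence as the proportion of entered patients with an event. Let p be the true incidence among all eligible admissions. Let r be the chance that a file with an event is entered, divided by the chance that a file without one is entered. Then

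observed incidence = p·r / (p·r + 1 − p).

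The ratio r multiplies the odds of an event. For rare events that is close to multiplying the incidence itself.

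**Worked case, p = 5%.**

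- r = 0.5: 0.025 / (0.025 + 0.95) = 2.56%
- r = 0.8: 0.040 / (0.040 + 0.95) = 4.04%
- r = 1: 5.00%
- r = 1.25: 0.0625 / (0.0625 + 0.95) = 6.17%
- r = 2: 0.10 / (0.10 + 0.95) = 9.52%

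**Range over p.**

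| True incidence | r = 0.5 | r = 0.8 | r = 1.25 | r = 2 |
|---|---|---|---|---|
| 2% | 1.01% | 1.61% | 2.49% | 3.92% |
| 5% | 2.56% | 4.04% | 6.17% | 9.52% |
| 10% | 5.26% | 8.16% | 12.20% | 18.18% |

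**Confidence intervals.** The plan promises 95% intervals without naming a method. With Wilson intervals and exact binomial probabilities at a true 5%, the interval contains the truth with these probabilities:

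| r | N = 200 | N = 500 | N = 1000 |
|---|---|---|---|
| 1 | 96.7% | 95.0% | 95.0% |
| 0.5 | 75.6% | 21.8% | 1.9% |
| 2 | 27.7% | 1.9% | about 0% |

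A larger sample does not help. It narrows the interval around the shifted value.

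**What a count of eligible patients would add.** Suppose 70% of eligible files are entered and show an incidence of 2%. If the other 30% have an incidence between 0% and 10%, the incidence in all eligible patients lies between 0.7 × 2% + 0.3 × 0% = 1.4% and 0.7 × 2% + 0.3 × 10% = 4.4%. Bounds of this kind need the 70%, and the plan does not ask for it.

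**The case against.** The strongest reply is that the text leans towards complete entry. It calls the study a cohort, fixes a one-year calendar window, screens files against criteria, and mentions no quota or investigator's choice. The document is also headed as a synopsis, which may leave out site logs and source lists. Both points stand in part: complete entry may well be what the sponsor intends. But no sentence requires it and nothing makes it checkable. The statement that all the data come from medical records describes the source of the data, not the completeness of the patients.

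A second reply is that visible outcomes are inherent in chart review, and that the imaging and bleeding definitions limit discretion in recording events. That is fair for how an event is classified. It does not bear on whether the file is entered.

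A third is that the sizes are hypothetical. That stands. Neither p nor r is in the documents, the direction is unknown, and r need not be the same for thrombosis and bleeding, or for major and minor events. With mild selection the shift is modest.

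The plan's own caution, under Statistical analysis, is about correlations and does not reach the incidence estimates.

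Three stronger readings are tempting, and the documents do not support them:

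- A reader might infer that the problem could never be detected afterwards. Pharmacy or admission records would allow eligible patients to be counted later; the plan simply does not ask for the count.
- A reader might infer that complete file entry would remove all selection. Signed consent is an entry criterion, consent may be related to outcome (most plainly through death), and the criteria make no provision for patients who died.
- A reader might infer that fixing file selection also deals with physicians recording events whose outcome they know. It does not change who completes the CRFs.

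**Conclusion.** The point holds as a gap in the design wording, and should be fixed. The plan defines eligibility but does not require complete or random entry of eligible admissions, and files are screened with the outcome known. Both primary incidences can therefore be shifted, in either direction, by the choice of files. As planned, the shift would go unnoticed because patients who were eligible but not entered are not counted.

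The size cannot be established from the documents. For an assumed true incidence of 5%, mild selection (r = 0.8 to 1.25) moves the estimate to between 4.0% and 6.2%, and twofold selection in either direction moves it to between 2.6% and 9.5%. Nothing in the documents shows that sites will select files, and the figures should not be read as a forecast that they will.

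**What to change.** Add to Study Design and to the screening step:

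- Before any chart is opened, each hospital lists all adult PCR-positive admissions in the one-year window with tinzaparin dispensed, from pharmacy or admission records.
- Every eligible patient on the list is entered. A site that cannot enter all of them enters a random sample drawn centrally from its list.
- Each site keeps a log of patients listed, screened, ineligible (by criterion), without consent (as its own category, including patients who died), and not entered. The log is reported as a flow table by hospital.

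State in the report that the incidences apply to consenting patients and that selection through consent remains.

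The cost is a protocol paragraph, one list and one log per site, and more files to screen. No endpoint or test changes. The list should be made before abstraction begins, because choices that were not logged are hard to reconstruct.

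### Associations with in-hospital events may use marker values taken after the event, and total prophylaxis duration, which grows with stay and can be cut short by the event

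*Combined protocol and SAP*

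**What the plan says.** All references are to the combined protocol and SAP.

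- **Study Design** commits to assessing the "association of a panel of laboratory and clinical parameters representing an inflammatory and hemostatic state with VTE and bleeding events and clinical outcomes". It also aims to look for associations of patients' "profiles with thrombotic and bleeding events and the course of illness in this cohort of patients".
- **Basic/common markers/parameters** lists the panel, which includes hemoglobin, and says that "laboratory and clinical parameters will be collected at 3 time points: at admission/baseline, after one week and at discharge". **Timepoints of evaluation** adds "Visit 2 - will be after 1 week", with a window of 2 days either way.
- **Data collection** sets the event window: "Thrombotic & bleeding events during course of hospitalization". Length of stay varies by patient and is a secondary endpoint.
- **Secondary Objectives** records "anticoagulant prophylaxis dose & duration" and says the study will "examine correlations between thromboprophylaxis approach", patient profiles and clinical outcomes.
- **Statistical and Analytic Plan** gives a list of items to be related to the primary and secondary outcomes; type and duration of prophylaxis is one of them. It names chi-square, Fisher, t-test, ANOVA, Mann-Whitney, a Cochran-Mantel-Haenszel odds ratio and logistic regression. It leaves room for further methods, sets p<0.05 as significant, and restricts correlations to assessing hypotheses.
- **Safety Evaluations** makes a hemoglobin fall of 2 g/dL or more one route to major bleeding, and stopping treatment, even temporarily, one of several routes to CRNMB.
- **Exclusion Criteria** removes "Current diagnosis or suspicion of pulmonary thromboembolism or deep vein thrombosis" at entry.

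**The concern.** The collection times are fixed, but the value to be analysed is not. An analyst who follows the text may relate any of the three marker values to an event at any point in the stay. A value taken after the event may be its consequence.

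Two of the plan's own definitions make this concrete. Hemoglobin is a panel marker, and a fall in it helps define major bleeding. Duration is a listed characteristic, and stopping the drug helps define CRNMB. Duration also grows with stay, and so does the time in which an event can occur.

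At stake are the exploratory associations, which are a stated aim of the study. The hypotheses they suggest could be products of event order or length of stay.

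**Working it through.** **1. Inputs.** The documents give no sample size, event rate, expected stay or stopping fraction, so there is no planned figure to reproduce. Every number below rests on assumed inputs, except alpha = 0.05.

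**2. Time order of the three marker values.**
- Admission: before any VTE counted in the study, because current or suspected PE/DVT is excluded.
- Week 1: before some events and after others.
- Discharge: after every in-hospital event in patients who are discharged.

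**3. Duration and time at risk.** Take a constant daily hazard h, unrelated to prophylaxis, so that risk = 1 - exp(-h × days). With h = 0.002, 7 days gives 0.0139 and 14 days gives 0.0276. The odds ratio is (0.0276/0.9724)/(0.0139/0.9861) = 2.01, although the daily rate ratio is 1.00.

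**4. Direction for duration.** Assume gamma stay with mean 10 days and shape 4, and a small constant hazard. The chance of an event is then roughly proportional to stay.
- Mean stay in event patients is about 10 × (1 + 1/4) = 12.5 days.
- The event falls on average halfway through, at 6.25 days.
- Mean stay in the others is about 10 days.

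If the drug stops at a fraction s of events, mean duration in event patients is about 12.5 - 6.25s:

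| s | 0 | 0.25 | 0.40 | 0.50 | 0.75 | 1 |
|---|---|---|---|---|---|---|
| Days | 12.5 | 10.9 | 10.0 | 9.4 | 7.8 | 6.25 |

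The sign changes at s = 0.40. In simulation with mean stay 7-14 days, the odds ratio per 7 days of prophylaxis is 1.19-1.49 at s = 0.25 and 0.78-0.89 at s = 0.50, with no true effect in either case.

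**5. Rejection rates for duration.** Null simulation with the same stay distribution (minimum 1 day), exponential event times, hazard solved for the stated incidence, and 1,500 runs per cell. Duration is the event time in a random fraction s of events and the full stay otherwise. Percentage of t-tests with p<0.05, for n = 300/600/1,000:

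| Incidence | s=0 | s=0.25 | s=0.50 | s=0.75 | s=1 |
|---|---|---|---|---|---|
| 1% | 15/23/33 | 9/11/15 | 10/11/11 | 14/23/32 | 25/46/68 |
| 3% | 31/56/74 | 14/17/22 | 13/13/18 | 29/47/66 | 60/86/98 |
| 6% | 52/81/96 | 16/23/33 | 14/16/22 | 46/69/88 | 87/99/100 |

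A separate simulation of the same cases gave 9-34% at s = 0.25 and 8-18% at s = 0.50, so about 8-34% covers both columns. With shapes 2-8 and mean stay 7-14 days (n = 600, 3%), the rates are 11-48% and 12-47%.

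**6. Markers measured after the event.** Null simulation with n = 300 or 700, h = 0.002 or 0.005, mean stay 10 days, and a marker that does not influence the event but is shifted 0.5-1.0 SD by it. The t-test rejects in 21-100% with the discharge value, about 10-83% with the week-1 value, and 4-7% with the admission value.

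For hemoglobin (n = 600, 1% major bleeding, SD 1.5-2.0 g/dL, half of major bleeds meeting the 2 g/dL criterion), the discharge value gives 11-38% if 1-2 g/dL of the fall remains. It gives about 5% if hemoglobin has fully recovered.

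**7. Admission markers and unequal stay.** Let an admission marker correlate 0.4 with stay and have no effect on the daily hazard (incidence 3%, mean stay 10 days, shape 4). True in-hospital incidence by marker tertile is then 2.4%, 3.0% and 3.6%. A test that rejects here detects a real difference in risk by discharge, which arises through stay.

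**The case against.** The strongest objection concerns time at risk. A reader might infer that every named test is wrong because stays differ, and that a time-to-event model must replace them. The documents do not support that. The endpoint is incidence during hospitalization, a window observed in full for each patient. Comparing that risk by admission marker or starting dose is a legitimate estimand, as step 7 shows. This part of the objection stands. A rate per patient-day answers a different, complementary question.

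A second stronger reading is that the plan will use discharge values to explain events. It does not say so; it only fails to exclude it. It labels the admission value as baseline, and the marker panel is also to be related to clinical outcomes, for which later values can be legitimate.

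The duration reading is also an inference. The list in the Statistical and Analytic Plan mixes patient characteristics with enrolment counts, therapy outcomes and complications, and may partly be a reporting list. Prophylaxis approach need not mean days of treatment. Still, the list is introduced as items to be related to the outcomes, and the primary outcomes are these events.

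The figures are wide and assumed. At s = 0.40 the means are equal, yet the t-test still rejects in about 8-12%, because durations are more spread out in the small event group. Some of the excess near that point is therefore not directional.

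Finally, the open clause on methods permits better analyses, and correlations serve only to assess hypotheses. Both lower the severity. Neither calls for a time-ordered analysis or removes the artefact.

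**Conclusion.** The concern holds for time order and for total duration. As written, the plan permits marker values taken after the event and, on its natural reading, relates total duration to events with tests that do not use event time. Either can yield an association with no true effect. For duration, the null rejection rate is about 8-34% if the drug stops at a quarter or half of events, and reaches 96% if it never stops and 100% if it always does. The sign depends on that fraction. These sizes rest on gamma stay with mean 10 days, incidence 1-6%, n = 300-1,000 and a constant hazard, none of which the documents give. The marker figures apply only if later values are used.

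A reader might infer that the main results are biased. They are not: the primary incidence estimates use neither marker timing nor duration. Severity is low to moderate, confined to exploratory results.

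**What to change.** State in the Statistical and Analytic Plan:

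1. Associations with in-hospital thrombotic and bleeding events use admission values.
2. Week-1 values are related only to later events, in patients still in hospital and event-free at that visit. Otherwise they are descriptive.
3. Discharge values and total prophylaxis duration are descriptive with respect to these events. They may still be related to status at discharge, such as the WHO score.
4. Prophylaxis is related to events by dose category at start.

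Keep the comparison of risk by discharge for admission markers and starting dose. Add event rates per patient-day as a supporting analysis, since part of a difference in risk may reflect length of stay. Record event dates and prophylaxis start, change and stop dates if the CRF, which is not shown, does not already hold them.

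**Cost.** A few sentences and slightly more chart abstraction; length of stay is already collected. Few events remain for a week-1 analysis. With n = 600 and 3% incidence there are 600 × 0.03 = 18 events. If 49-81% occur before day 7 (shape 4, mean stay 7-14 days, assumed), between 18 × 0.19 = 3.4 and 18 × 0.51 = 9.2 are left, so that analysis may have to stay descriptive. Dose at start ignores later changes and remains confounded by the risk-adapted choice of dose described in the Introduction.

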Introduction	
International guidelines recommend that hospitalized patients with COVID-19 should receive pharmacological prophylaxis against VTE, in the absence of contraindications [7,8,9]. With respect to how VTE prophylaxis is achieved, Low Molecular Weight Heparins (LMWH), in addition to their well-known anticoagulant properties, appear to have additional antiviral and anti-inflammatory effects that may be potentially beneficial in hospitalized COVID-19 patients. [10,11].
 
Though international and national guidelines states that all hospitalized patients with COVID-19 should receive pharmacologic thromboprophylaxis, the rising incidence of thrombotic complications in COVID-19 patients has led a lot of hospitals to adopt the strategy of increasing the dose of anticoagulation for prophylaxis to 'intermediate' or "therapeutic" doses using a risk-adapted strategy with increased doses administration based on factors associated with increased risk; clinicians weigh the benefits and risks of therapeutic anticoagulation in terms of thrombosis and major bleeding risk for individual patients.
 
Additionally, LMWHs have different physiochemical characteristics as a result of the diverse methods of their manufacturing. The variations in molecular composition and pharmacological properties of LMWHs are reflected in differences in their clinical efficacy and safety. Each LMWH should, therefore, be considered as a unique substance. Tinzaparin is the only LMWH known that is prepared by enzymatic hydrolysis with heparinase [12,13,14,15]. Due to its preparation method, tinzaparin has distinct properties than other LMWHs including and not limited to: higher Anti-IIa activity and Anti-Xa/Anti-IIa activity ratio, higher release of Tissue Factor Pathway Inhibitor (TFPI), less dependence from renal function for its clearance and more complete neutralization from its antidote, if needed. Due to the key role of increased Thrombin generation (IIa) and Tissue factor (TF) pathway activation in COVID-19-associated thrombosis [16], special properties of tinzaparin in Anti-IIa activity and TFPI production and release from endothelial cells, as well as significant effects of TFPI in various vascular, inflammatory, cardiovascular, hematological and oncological disorders [17,18,19,20,21], tinzaparin could have an expanded role beyond its well-known anticoagulant function.
 
The purpose of this study is to evaluate the overall clinical effectiveness and safety of 'intermediate' or "therapeutic" doses anticoagulation with tinzaparin administered for thromboprophylaxis in COVID-19 patients with moderate disease severity during hospitalization in Greek hospitals.

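### The primary incidences have no index time tied to the raised dose, so where dosing starts after admission they can include events and days that precede the studied exposure

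*Combined protocol and SAP*

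**What the plan says.** - **Entry.** Subject Population, inclusion criterion 1, takes patients with confirmed infection "administered thromboprophylaxis with tinzaparin in intermediate or therapeutic dose". It sets no start window, no minimum duration and no rule on earlier treatment at another dose or with another heparin.
- **Exposure period.** Study Design describes tinzaparin given "according to current clinical practice, during hospitalization, for one year before the study initiation date". That places the exposure within the stay but not at its start.
- **Baseline.** Study Phases, Timepoints of evaluation, has "Visit 1 – Baseline, at admission". No other time origin is defined.
- **Event window.** Study Phases, Data collection, lists "Thrombotic & bleeding events during course of hospitalization".
- **Primary objectives.** These are the "incidence of thrombotic events" and the "incidence of bleeding events". Neither they nor the matching endpoints carry a denominator, a risk window or person-time.
- **Safeguard.** Exclusion criterion 4 removes patients with current or suspected pulmonary embolism or deep vein thrombosis, but does not say as of when. Exclusion criterion 5, by contrast, is dated to admission.
- **Exposure data.** Study Objectives names dose and duration of prophylaxis, and the data collection list has a general anticoagulant item. A start date is not named.
- **Analysis.** The Statistical and Analytic Plan offers chi-square and Fisher tests, t-tests, ANOVA, Mann-Whitney tests and logistic regression. It has no landmark, on-treatment window or time-varying exposure.

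**The concern.** Three things should coincide in a single-exposure cohort: the time eligibility is met, the time exposure starts, and the time event counting starts. Here eligibility is met when the raised dose is given, while the only stated origin is admission and events are gathered from then on.

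The Introduction describes a risk-adapted policy in which clinicians weigh thrombosis against bleeding for each patient. Such a decision can be taken or revised during the stay. A patient treated at a standard dose, or with another heparin, for the first days and then moved to raised-dose tinzaparin satisfies inclusion criterion 1. A bleed on day 2 in that patient is then counted as a bleed in the raised-dose cohort. That sits badly with the Introduction's own view that "Each LMWH should, therefore, be considered as a unique substance".

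Conversely, a patient whose early event stopped any escalation never enters, so those who do enter have waiting time that is event-free by construction.

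Both primary endpoints are affected, and there is no comparator in which the same error might cancel. If start and onset dates are not abstracted, no later analysis can separate the two periods.

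**Working it through.** The documents state no sample size, expected rate, event count or start-time distribution, so there is no figure of the plan's to reproduce. What follows uses assumed inputs, only to show how the result depends on the start delay.

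**Assumptions.** Stay of 10 days. Raised dose starts *d* days after admission. Constant daily hazard *h0* before the raised dose and *h1* on it.

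**Case 1: events before the start are counted** (the literal reading of the event window).

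- Incidence over the stay: A = 1 − exp(−h0·d − h1·(10 − d))
- Part arising before the start: P = 1 − exp(−h0·d), with share P/A
- Incidence after the start: B = 1 − exp(−h1·(10 − d))

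With h0 = 0.004, h1 = 0.002 and d = 3:

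- A = 1 − exp(−0.012 − 0.014) = 2.57%
- P = 1 − exp(−0.012) = 1.19%, so P/A = 46%
- B = 1 − exp(−0.014) = 1.39%

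| d (days) | Unexposed share of stay | A, whole stay | Share before start | B, after start |
|---|---|---|---|---|
| 0 | 0% | 1.98% | 0% | 1.98% |
| 1 | 10% | 2.18% | 18% | 1.78% |
| 3 | 30% | 2.57% | 46% | 1.39% |
| 5 | 50% | 2.96% | 67% | 1.00% |

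If the hazard is 0.004 throughout, A is 3.92% at every delay. The share before the start is 10%, 30% and 50% for d = 1, 3 and 5, and B is 3.54%, 2.76% and 1.98%.

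**Case 2: patients with an event before the start never enter.** The per-patient incidence is then B, which is correct for the days after the start. A rate per person-day counted from admission is diluted, because *d* event-free days per patient enter the denominator:

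- rate from admission = B / (d + B/h1)

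For d = 3 and h1 = 0.002 this is 0.01390 / (3 + 6.95) = 0.00140 per day, which is 0.70 of the on-dose rate. For d = 1 and d = 5 the ratios are 0.90 and 0.50. They are the same to two decimals when h1 = 0.004.

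For any one event, Cases 1 and 2 are alternatives. They push in opposite directions, and the text does not say which applies.

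**The case against.** The strongest reply is that late starts are inferred from silence. Nothing in the documents shows that hospitals delayed the raised dose, and if it began at admission there is no error. The admission baseline is also a data-collection visit, and the whole-stay event item is a collection item, not an endpoint definition. All of this is fair, and it limits the point to what the text permits. But no other origin or window is given, so an analyst following the plan would use these.

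A second reply is that the primary objective concerns a management approach, so counting events after a switch to another drug is a legitimate strategy-level measure, and the sentence on unique substances is background and not an attribution rule. That stands for events after the start. It does not rescue events before it: a strategy followed from admission would also have to include patients who were never escalated, and inclusion criterion 1 leaves them out.

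Two stronger readings are tempting.

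- **A reader might infer that the cohort is filled with patients whose dose was raised because of a thrombosis.** The documents do not support that. Inclusion criterion 1 is limited to thromboprophylaxis, so a dose given to treat a clot does not qualify on its ordinary reading, and exclusion criterion 4 points the same way. What remains is narrower: *current* has no reference date, so a PE or DVT arising in hospital before the raised dose is not clearly excluded, and chart reviewers have no rule for telling prophylaxis from treatment. The number of such patients cannot be derived.
- **A reader might infer that bleeding is necessarily understated.** At an assumed 0.5% per day, 1 − 0.995^10 = 4.9% over 10 days and 1 − 0.995^7 = 3.4% over the 7 days after a day-3 start. But 3.4% is the correct risk for those 7 days, and moving the index time leaves it unchanged. It misleads only if reported as risk from admission. If a patient bleeds and is escalated later, the error goes upward.

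Finally, dose and duration are already to be recorded, and correlations are to be interpreted cautiously. Duration without a start date does not place an event before or after exposure, and the caution concerns correlations, not the primary incidences.

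**Conclusion.** The point holds in a bounded form. The text allows raised-dose tinzaparin to start at any time in the stay while the only baseline is admission and events are collected throughout. Both primary incidences can therefore include events from before the exposure, and any figure stated from admission includes unexposed or event-free waiting time.

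The direction is not fixed: upward where earlier events are counted and the prior hazard is higher, downward for an admission-based rate where earlier events bar entry. In the assumed 10-day stay, delays of 1 to 5 days put 18% to 67% of the counted incidence before the exposure (10% to 50% with equal hazards), or reduce an admission-based rate to 0.90 to 0.50 of the on-dose rate. These are illustrations, not estimates for this study. The true size depends on local escalation practice and is zero if dosing began at admission. The exposure to error through event-triggered dosing is confined to the undated exclusion criterion 4.

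**What to change.** 1. Record on the CRF the start and stop dates of raised-dose tinzaparin and the onset date of every thrombotic and bleeding event, with times where the chart gives them.
2. Define the index time as the first administration of intermediate- or therapeutic-dose tinzaparin in the stay.
3. Apply exclusion criterion 4 as of the index time.
4. In the primary incidences, count only events with onset after index, from index to discharge.
5. List events between admission and index separately.
6. Add a secondary figure limited to time on raised-dose tinzaparin, with person-days as denominator.

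Report the distribution of time from admission to index as well, since it shows directly whether the issue was material.

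The cost is a change of protocol wording and slightly more chart abstraction, within an anticoagulant data item already planned. A few pre-index events leave the primary count, and patients with a PE or DVT at index leave the cohort. The study is retrospective, so nobody's treatment is affected. The change should be made before abstraction begins, because dates not collected then would mean going back to the charts.
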